# 5.7.1.2 Pharmacodynamics

Pharmacodynamic parameters are not evaluated in this study.

## 5.7.1.3 Genomics

Genetics are not evaluated in this study.

#### 5.7.1.4 Immunogenicity

### Anti-bimekizumab antibodies

The ADAb will be assessed using a 3-tiered assay approach: Screening, confirmatory, and

Screening, confirmatory and titer cut points of the respective assays will be determined by the bioanalytical laboratory. The relevant statistical reports will be provided as part of the bioanalytical reports.

ADAb samples are analyzed on the SS but are only analyzed for study participants on bimekizumab.

The Screening cut point will be used to determine the ADAb status in the test sample as "Positive Screen" (PS) or "Negative Screen" (NS). For samples presenting anti-bimekizumab antibody levels that are PS, further confirmatory assay will be performed, and the result of which will be reported as either "Positive Immunodepletion" (PI) or "Negative Immunodepletion" (NI).

The ADAb status for each visit will be derived as following:

- ADAb negative sample values that are either NS or PS and NI.
- Inconclusive sample values that are either NS or PS and NI and where the bimekizumab concentration exceeds the validated ADAb assay drug tolerance limit.
- ADAb positive sample values that are PS and PI (regardless of availability of a titer value).
- Missing if sample is not in one of the above categories.

For the overall ADAb status, a study participant will be classified as follows, excluding any assessments at SFU:

- **Positive** if the study participant has at least 1 positive sample at any time in the treatment _ period (regardless of having missing/inconclusive data).
- Negative if the study participant has all their samples negative or only 1 missing/inconclusive sample with all other negative ADAb samples.
- **Missing** if the study participant has missed more than 1 sample result for ADAb assessment (or have more than 1 inconclusive sample) and all other available ADAb samples are negative during the period of interest.

PI samples will be titrated and the ADAb titer reported. The PI samples will also be subject to a neutralizing (NAb) assay to evaluate whether the anti-bimekizumab antibody neutralizes the target binding of bimekizumab (IL17A or IL17F or both) in-vitro.

The following rule will be implemented for by-visit ADAb summaries where applicable:

- If the ADAb sample is collected within  $\pm 14$  days (excluding the SFU visit) relative to the visit date at which the drug was administered, the ADAb result for that sample will be associated with the scheduled visit and summarized accordingly.
- In all cases, this will include unscheduled assessments (if a dose was administered at an unscheduled visit).

Summaries of cumulative ADAb status and time to treatment-emergent positivity will use all available data.

In addition, the ADAb status will be further classified according to the following ADAb categories:

- ion Category 1: Pre ADAb negative - treatment-emergent ADAb negative: Includes study participants who are negative at Baseline and antibody negative at all sampling points post treatment (excluding SFU). This group also includes study participants who have missing/inconclusive pre-treatment sample (e.g. either missing/inconclusive or insufficient volume) at baseline with all post-baseline samples as ADAb negative.
- Category 2: Pre ADAb negative treatment-emergent ADAb positive: Includes study participants who are negative at Baseline and antibody positive at any sampling point post treatment (excluding SFU). This group also includes study participants who have a missing pre-treatment sample (either missing or insufficient volume) at Baseline with one or more ADAb positive post-treatment samples.
- Category 3: Pre ADAb positive treatment reduced ADAb: Includes study participants who are positive at Baseline, and antibody negative at all sampling points post treatment (excluding SFU).
- Category 4: Pre ADAb positive treatment unaffected ADAb positive: Includes study participants who are positive at Baseline and are positive at any sampling point post treatment (excluding SFU) with titer values of the same magnitude as Baseline (i.e. less than a predefined fold difference from the Baseline value). For the purposes of this study, this is set at an increase of less than the validated Minimum Significant Ratio (MSR) from baseline.

Category 5: Pre ADAb positive - treatment boosted ADAb positive: Includes study participants who are positive at Baseline and are positive at any sampling point post treatment (excluding SFU) with increased titer values compared to Baseline (greater than or equal to a predefined fold difference increase from Baseline value which is defined within the validation of the assay). For the purposes of this study, this is set at an increase greater than or equal to the validated MSR from Baseline.

Note: For any study participant who is positive at Baseline and positive at a post-Baseline time point, but for whom titers are not available to determine treatment unaffected or treatment boosted status, the study participant will be considered as treatment boosted assuming no other samples are available.

Category 6: Inconclusive: Includes study participants who have a positive pre-treatment sample and some post-treatment samples are missing, while other post-treatment samples are ADAb negative.

- **Category 7: Total treatment-emergent:** Category 2 and 5 combined: Includes study participants who are pre ADAb negative – treatment emergent ADAb positive (Category 2) and pre ADAb positive – treatment boosted ADAb positive (Category 5).
- Category 8: Total prevalence of pre-ADAb positivity: (Categories 3, 4, 5 and 6 combined): Study participants that are tested ADAb positive at Baseline.

Category 9: Missing: Includes study participants who have a negative or a missing/inconclusive pre-treatment sample and some post-treatment samples are missing/inconclusive, while other post-treatment samples are ADAb negative.

The following analyses will be prepared on the SS:

- ion A summary table displaying the number and percentage of study participants with ADAb status (positive, negative or missing) at each visit (excluding SFU) and overall. The overall summary will be presented for both visit during the treatment period and any visit during the study (including Baseline but excluding the SFU visit).
- A table displaying the number (%) of study participants with the first occurrence of ADAb treatment-emergent positivity during the study (i.e., including Baseline visit) will be summarized. This summary will include the following categories:
  - Any ADAb+: ADA positive sample regardless of category during the treatment period,
  - ADAb Category 2: Pre ADAb negative treatment-emergent ADAb positive,
  - ADAb Category 5: Pre ADAb positive treatment-boosted ADAb positive (if this category represents at least 10% of the study participants, otherwise results are to be merged with Category 2). For this category, the first occurrence of a boosted result is considered.

The table will include the number and percentage of study participants with first occurrence of any ADAb+ sample, and also study participants who are either treatment-emergent ADAb positive or treatment-boosted ADAb positive for the first time at the specified time point in the study and will include the cumulative number and percentage of study participants with any ADAb+ sample and treatment-emergent ADAb positive results at each time point.

- A boxplot of the ADAb titer by time of occurrence of ADAb positivity will be created. The ADAb titer results will be presented on the log-scale. The time to occurrence is defined as the time in weeks from Baseline until the visit of interest when a sample is ADAb positive. Study participants who do not have any ADAb positivity will be excluded from the plot.
- A summary table of the number and percentage of study participants in each of the 9 ADAb categories will be tabulated.
- The time to achieving treatment-emergent anti-bimekizumab antibody positivity, separated by treatment group and Categories 2 & 5 above, will be analyzed based on Kaplan-Meier methods. Participants will be considered to have an event at the time point at which treatment emergent anti-bimekizumab antibody positive is first achieved (taking the MSR into consideration for Category 5). Participants classified as treatment-emergent ADAb negative will be censored at the time of the last available ADAb result.
- Individual plots (one plot by study participant) of bimekizumab concentrations/ADAb titer (log-scale) and PASI % change from baseline will be created. All 3 endpoints will be plotted on the Y-axis by visit (x-axis) for the full treatment period, including the SFU. Plots should be labeled and grouped into the 9 ADAb categories and display vertical tick-marks on the xaxis corresponding to dosing events.

- A spaghetti plot of ADAb titer (log-scale) by visit (x-axis) will be presented for all ADAb positive study participants defined as being in Categories 2 & 5 above:
- A figure will summarize efficacy response (PASI75, PASI90 and PASI100 responders) versus ADAb titer quartiles. The x-axis will display the ADAb titer quartiles at Week 16 (categorized as negative, Q1, Q2, Q3 and Q4) and the y-axis will display percentage of PASI75/90/100 responders at Week 16.
- Stion Three figures (side by side) summarizing the time course of efficacy response (PASI75 PASI90 & PASI100 responders at Week 16) by overall ADAb status (3 lines per plot) will be created.

The missing group will not be displayed on the figure if the group represents <5% of study participants.

- Finally, all individual study participants-level ADAb results (including SFU) will be listed including the Screening assay, confirmatory assay, ADAb status, and titers if applicable. NB: titer results will only be available if the confirmatory assay is positive. The listing will also include flags for ADAb measurements that were excluded from the by-visit summaries. The reason for exclusion will be one of the following:
  - Sample collected out of window relative to current dose (or visit),
  - More than one sample obtained at the same visit. _

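### The Kaplan-Meier analysis of time to ADAb positivity is grouped by categories that require the event and censors only Category 1: Category 5 is wrong whether the categories are strata or event types, Category 2 only if they are strata

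*SAP*

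**What the plan says.** All of the text is in SAP section 5.7.1.4, under anti-bimekizumab antibodies.

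- **Grouping.** Time to treatment-emergent positivity, "separated by treatment group and Categories 2 & 5 above, will be analyzed based on Kaplan-Meier methods".
- **Event.** "Participants will be considered to have an event at the time point at which treatment emergent anti-bimekizumab antibody positive is first achieved", with the minimum significant ratio (MSR) taken into account for Category 5.
- **Censoring.** "Participants classified as treatment-emergent ADAb negative will be censored at the time of the last available ADAb result". This is the only censoring rule.
- **Category 1**, whose title carries the label used in that rule, holds "participants who are negative at Baseline and antibody negative at all sampling points post treatment (excluding SFU"), plus people with a missing or inconclusive Baseline sample and only negative samples afterwards.
- **Category 2** holds "participants who are negative at Baseline and antibody positive at any sampling point post treatment (excluding SFU"), plus people with a missing Baseline sample and a later positive.
- **Category 5** is Baseline positive with a raised titer; "this is set at an increase greater than or equal to the validated MSR from Baseline". A Baseline-positive participant with a later positive but no titers is also counted as boosted.
- **Category 3** holds "participants who are positive at Baseline, and antibody negative at all sampling points post treatment (excluding SFU"). Category 4 is Baseline positive and later positive without a rise of that size. Category 6 is Baseline positive with some later samples missing and the rest negative.
- **Category 9** is Baseline negative, missing or inconclusive, with some later samples missing or inconclusive and the rest negative.

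ADAb samples "are only analyzed for study participants on bimekizumab". The first-occurrence table described just before the Kaplan-Meier item uses Categories 2 and 5 as kinds of event. It merges Category 5 into Category 2 when Category 5 holds under 10% of participants.

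**The concern.** A Kaplan-Meier curve needs a risk set of people who could have the event, some of whom may not. Categories 2 and 5 are assigned after the fact and require the event, so they cannot serve as risk sets. The group named for censoring lies outside both. The grouping sentence and the censoring sentence therefore do not describe the same set of people, and the plan does not say which governs.

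Two programmers could draw materially different curves from the same data. For Category 5, neither the strata reading nor the event-type reading gives the incidence of boosting among people who could be boosted. At stake is one displayed immunogenicity time course in a study meant to support bridging.

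**Working it through.** The documents give no ADAb rate and no figure for this analysis, so there is nothing to reproduce. The only input from the plan is the 30 bimekizumab participants (SAP section 3). The category counts below are assumptions, chosen to cover a range and each adding to 30. Category 9 is set to zero in them.

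The estimate is 1 − S(t), with S(t) = Π(1 − d/n) over event times. Events are placed at Weeks 4, 8, 12 and 16, and non-events are censored at Week 16. With no earlier censoring, the Week 16 value reduces to events / (events + censored).

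**Reading A: categories as strata.** Everyone in the stratum has the event, so at the last event time d = n and the curve ends at 100%. This holds for both categories in every assumed set. The censoring sentence has nobody to act on.

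**Reading B: categories as event types, Category 1 censored.** Counts are in the order Category 1 / Category 2 / Baseline positive not boosted (Categories 3, 4, 6) / Category 5.

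| Assumed counts | Category 2 curve = baseline-negative risk set | Category 5 curve as written | Baseline-positive risk set |
|---|---|---|---|
| 24 / 3 / 2 / 1 | 3/27 = 11.1% | 1/25 = 4.0% | 1/3 = 33.3% |
| 16 / 10 / 3 / 1 | 10/26 = 38.5% | 1/17 = 5.9% | 1/4 = 25.0% |
| 12 / 12 / 3 / 3 | 12/24 = 50.0% | 3/15 = 20.0% | 3/6 = 50.0% |
| 8 / 14 / 4 / 4 | 14/22 = 63.6% | 4/12 = 33.3% | 4/8 = 50.0% |

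The Category 2 curve is right in all four sets: Category 1 participants could have converted and did not, which is ordinary censoring. The Category 5 curve is too low in all four. Category 1 is not at risk of a boost, and the people who were at risk and not boosted have no rule.

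**Reading C: Categories 2 and 5 pooled, Category 1 censored.** This gives 4/28 = 14.3%, 11/27 = 40.7%, 15/27 = 55.6% and 18/26 = 69.2%. With the non-boosted Baseline-positive participants kept as censored, the values are 4/30 = 13.3%, 11/30 = 36.7%, 15/30 = 50.0% and 18/30 = 60.0%. The pooled curve is therefore too high by 1.0 to 9.2 points.

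**Category 9.** These people belong in the Baseline-negative risk set but are not named. If a fraction q of the participants without the event were dropped for that reason and the true incidence were 40% (both assumed), the curve would read 0.4 / (0.4 + 0.6(1 − q)). That is 42.6%, 45.5% and 48.8% for q = 10%, 20% and 30%.

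**The case against.** The strongest case against is that the strata reading is not what the SAP intends. A censoring rule makes sense only if people without the event are in the analysis, the event sentence singles out Category 5 for the MSR, and the neighbouring table treats both categories as event types. This stands. A reader might infer that every reading fails, or that the plan would report 100% where the truth is, say, 40%. The documents do not support either. The 60-point gap arises only under strata, and on the event-type reading Category 2 is sound.

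A reader might also infer that Category 2 is diluted by Baseline-positive people (40% reading as 36% if 10% are Baseline positive: 0.4 × 0.9). That requires the censoring label to cover everyone without the event, whereas the SAP gives the label to Category 1 alone. Even so, the wider reading would not rescue a separate Category 5 curve: in the first assumed set it gives 1/(24 + 2 + 1) = 3.7% against 33.3%.

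The SAP says that summaries of time to positivity use all available data. That sentence follows the sample-window rule and sets no censoring time, but it does count against dropping Category 9. No text says to drop those participants.

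If the table's 10% merge rule carried over, Category 5 (1/30 = 3.3%) would not be shown separately in the first two sets, and the error would shrink to the pooled one. The rule is not restated for the curve, and the other two sets (3/30 = 10.0%, 4/30 = 13.3%) would not trigger it.

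Finally, incidence is also reported in the first-occurrence table, with cumulative percentages by time point, and in the counts for all nine categories. A misleading curve would be visibly at odds with them. That limits the harm but does not make the curve right.

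**Conclusion.** The point holds in a limited form and is minor. The grouping and the sole censoring rule do not fit together. Category 5 comes out wrong whether the categories are strata (100% by construction) or event types (4.0% to 33.3% against 25.0% to 50.0% in the assumed sets). Category 2 is wrong only under strata; under event types its one gap is that Category 9 is unnamed. Every count and rate is an illustrative assumption, and the Category 5 comparisons rest on three to eight Baseline-positive people.

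No test depends on this output: it is descriptive and serves a tertiary objective, and the co-primary analyses and sample size are untouched. Separation by treatment group yields a single group because only bimekizumab participants are analyzed; it is redundant and biases nothing.

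**What to change.** Rewrite the Kaplan-Meier item so that risk sets follow Baseline ADAb status:

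- **Baseline negative, missing or inconclusive:** the event is the first positive result (Category 2). Categories 1 and 9 are censored at the last evaluable ADAb result. Category 2 now names a missing Baseline sample but not an inconclusive one, so state that the latter is included, in line with Categories 1 and 9.
- **Baseline positive:** the event is the first boost of at least the MSR (Category 5, keeping the existing convention for positives without titers). Categories 3, 4 and 6 are censored at the last evaluable ADAb result.
- **If one curve is preferred:** use the Category 7 event in all bimekizumab-treated Safety Set participants with at least one post-Baseline ADAb result, and censor everyone without the event.

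Say what counts as evaluable, state whether the 10% merge rule applies to the curve, and delete the reference to treatment group. The cost is SAP wording only, with the same data and the same procedure.

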#### Neutralizing anti-bimekizumab antibodies (NAbs) 5.7.2

NAbs will be assessed using IL-17AA- and IL-17FF-specific assay methods. NAb results will be positive or negative to each specific NAb assay or both.

Any NAb results derived from samples with drug concentrations > the drug tolerance limits of the NAb assays will be labeled "inconclusive". All inconclusive results will be regarded as missing.

Study participants will be assigned an overall NAb classification, inclusive of Baseline and post-Baseline results but excluding SFU as follows:

- NAb negative: No NAb positive samples for IL-17AA and IL-17FF at Baseline or post-Baseline. This group will also include study participants who have only 1 missing sample and all other available samples during the period of interest are negative. Study participants who are NAb negative will be classified as follows:
  - ADAb positive / NAb negative: ADAb positive study participants who are 1) NAb negative for all available ADAb positive samples or 2) with only one missing NAb sample and all other evaluated ADAb positive samples are NAb negative.
  - ADAb negative: if the study participant has all the samples as ADAb negative or only one missing/inconclusive sample with all other available samples as negative ADAb.
- NAb positive: One or more positive samples (IL-17AA positive, IL-17FF positive, or both) at Baseline or post-Baseline (regardless of missing samples). Study participants who are NAb positive will be further classified as follows:

- Positive for IL-17AA only: one or more positive samples for IL-17AA at baseline or post-baseline. No positive samples for IL-17FF
- Positive for IL-17FF only: one or more positive samples for IL-17 FF at baseline or postbaseline. No positive samples for IL-17AA
- Positive for both IL-17AA and IL-17FF: one or more positive samples for both IL-17A and IL-17FF at baseline or post-baseline
- NAb Missing: •
  - >1 relevant NAb samples are missing and other available NAb samples during the period of interest are negative, e.g., missing or insufficient sample left for NAb testing.
- A listing will be produced to summarize the NAb status overall in the study. The listing will ortany markins summarize the following information for each study participant assessed for Nab (including SFU data):
  - Subject identifier
  - Visit
  - Study week
  - Laboratory sampling date and time
  - Time since previous dose (weeks)
  - Bimekizumab plasma concentration level at visit (ug/mL)
  - ADAb titer at visit
  - IL-17AA NAb status and corresponding IL-17AA signal/negative control result
  - IL-17FF NAb status and corresponding IL-17FF signal/negative control result.
- A table will provide the following overall summary statistics:
  - The number and percentage (based on the total number of study participants randomized to bimekizumab) of study participants confirmed as ADAb positive and negative up to Week 16
  - The number and percentage (based on both the total number of study participants randomized to bimekizumab and the number of ADAb positive study participants) of study participants who are NAb positive, NAb negative and missing up to Week 16.

In addition, the following analysis will be performed to assess the impact of NAb status on efficacy measures:

Three figures (side by side) summarizing the time course of efficacy response (PASI75. PASI90 & PASI100 responders at Week 16) by NAb status (ADAb negative; NAb positive; ADAb positive/NAb negative; missing).

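### Read literally, the NAb table in SAP 5.7.2 counts ADAb-negative participants as NAb negative even on the ADAb-positive base, so that row can exceed 100% and the rows need not sum to 100%

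*SAP*

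**What the plan says.** SAP 5.7.1.4 (Immunogenicity) describes a tiered assay. On NAb testing it says: "The PI samples will also be subject to a neutralizing (NAb) assay". PI samples are those that screen positive and are then confirmed. Protocol 8.9 likewise sends only confirmed positive samples for neutralization testing.

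SAP 5.7.2 assigns each participant an overall NAb class, using Baseline and post-Baseline results but not the safety follow-up. The negative class opens: "NAb negative: No NAb positive samples for IL-17AA and IL-17FF at Baseline or post-Baseline". The section continues, "Study participants who are NAb negative will be classified as follows", and lists two sub-classes. The first is ADAb positive/NAb negative. The second reads: "ADAb negative: if the study participant has all the samples as ADAb negative or only one missing/inconclusive sample with all other available samples as negative" (the word ADAb completes the phrase). The NAb-missing class needs more than one relevant NAb sample to be missing, with the other available results negative.

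The summary table later in SAP 5.7.2 has two bullets. The first gives ADAb-positive and ADAb-negative counts as percentages of those randomized to bimekizumab. The second gives number and percentage on two bases. One is the whole randomized bimekizumab arm; the SAP words the other, together with the rows, as "and the number of ADAb positive study participants) of study participants who are NAb positive, NAb negative and missing up to Week 16".

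Elsewhere the SAP uses four groups: ADAb negative, NAb positive, ADAb positive/NAb negative, and missing. These appear in the PK summaries (SAP 5.7.1.1) and in the efficacy figures by NAb status (SAP 5.7.2).

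**The concern.** A percentage needs a numerator drawn from its denominator. On the ADAb-positive base, the NAb-negative row as defined brings in participants whom the denominator leaves out. A programmer who follows the definition and one who follows the evident intent would produce different tables, and only the first would match the SAP text.

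There is also a labelling problem on the all-bimekizumab base. An ADAb-negative participant has no confirmed-positive sample, so nothing is eligible for the NAb assay. The NAb-negative row there mixes participants tested and found negative with participants never tested.

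What is at stake is whether one descriptive immunogenicity table can be read. Immunogenicity is a tertiary objective, but the study supports a bridging submission (Protocol 4.2), and this is the only table in SAP 5.7.2 that gives overall NAb rates.

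**Working it through.** The documents state no antibody rate, so there is no planned figure to reproduce. The check applies the written rule to a range of assumed counts.

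**Inputs**
- N = 30 on bimekizumab (SAP Section 3, planned arm size).
- A = number ADAb positive, and q = number NAb positive. Both are assumptions.
- No missing or inconclusive results, for simplicity.

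**Step 1: who is NAb negative.** By the definition in SAP 5.7.2, NAb negative = ADAb negative + ADAb positive/NAb negative = (N − A) + (A − q) = N − q.

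**Step 2: ADAb-positive base, as written.** The NAb-negative row is (N − q)/A. It exceeds 100% when N − q > A, that is, when N − A > q: ADAb negatives outnumber NAb positives. The NAb-positive row is q/A. The two rows sum to N/A, which is above 100% whenever A < N.

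**Step 3: ADAb-positive base, restricted to ADAb-positive participants.** The NAb-negative row becomes (A − q)/A. It lies between 0 and 100%, and with q/A it sums to 100%.

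**Step 4: all-bimekizumab base.** The NAb-negative row is (N − q)/N, which cannot exceed 100%. The share tested and found negative is (A − q)/N.

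| A | q | NAb neg. as written, base A | Row sum, base A | Restricted, base A | NAb neg. as written, base 30 | Tested and negative, base 30 |
|---|---|---|---|---|---|---|
| 6 | 2 | 28/6 = 466.7% | 500.0% | 4/6 = 66.7% | 28/30 = 93.3% | 4/30 = 13.3% |
| 9 | 3 | 27/9 = 300.0% | 333.3% | 6/9 = 66.7% | 27/30 = 90.0% | 6/30 = 20.0% |
| 15 | 5 | 25/15 = 166.7% | 200.0% | 10/15 = 66.7% | 25/30 = 83.3% | 10/30 = 33.3% |
| 21 | 7 | 23/21 = 109.5% | 142.9% | 14/21 = 66.7% | 23/30 = 76.7% | 14/30 = 46.7% |
| 24 | 8 | 22/24 = 91.7% | 125.0% | 16/24 = 66.7% | 22/30 = 73.3% | 16/30 = 53.3% |

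The last line shows that the row itself need not pass 100%: 6 ADAb negatives do not outnumber 8 NAb positives. The rows still sum to 125%.

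**Step 5: could the missing class absorb the ADAb negatives?** No. It requires more than one relevant NAb sample to be missing, and on the natural reading an ADAb-negative participant has no relevant NAb sample. SAP 5.7.2 also places ADAb negatives under NAb negative in so many words.

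**The case against.** The best defence is that the written rule would not survive contact with real output. A percentage on a subset base ordinarily counts members of that subset. SAP 5.7.2 already defines the class needed, ADAb positive/NAb negative, and a figure such as 467% would be caught at the first dry run. On this view the bullet lacks a qualifier and nothing more. The point stands as far as likelihood goes: the impossible percentage appears only if the table is programmed literally. It does not remove the defect, because the SAP states a definition and a denominator that do not fit together, and the repair would be an unwritten departure from the prespecified text.

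The defence also notes that ADAb-positive and ADAb-negative counts sit in the same table, so a reader could largely separate untested participants from tested ones. That is fair. On the all-bimekizumab base the issue is a label, disclosed in the definition, and not an arithmetic error.

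A reader might infer that the NAb positivity rate is wrong. It is not: a NAb-positive participant must have a confirmed-positive ADAb sample, so q/N and q/A are both sound. Nor do comparisons by NAb status suffer, since the PK summaries and efficacy figures already use the four groups.

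A reader might also conclude that the all-bimekizumab base should move from randomized to treated participants. That is a separate question, and it has no bearing on the mismatch between numerator and denominator.

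**Conclusion.** The point holds for the NAb-negative row and the row total on the ADAb-positive base, and as a labelling matter on the all-bimekizumab base. It is a stated rule that gives a wrong result if followed, not just missing detail.

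Its size depends on antibody rates that the documents do not give. Over the assumed counts above, with 30 participants, one third of ADAb positives NAb positive and nothing missing, the row runs from 92% to 467% where 67% is meant. Row sums exceed 100% whenever anyone is ADAb negative.

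That the NAb-positive percentages are correct assumes that the ADAb-positive count covers Baseline as well as post-Baseline samples, as the NAb classification does. The table is descriptive: the co-primary tests, type I error, power and safety conclusions are unaffected. This is a worthwhile correction to one table and casts no doubt on the trial's conclusions.

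**What to change.** Amend the second bullet of the summary table in SAP 5.7.2.

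- **ADAb-positive base:** count only ADAb-positive participants, in three rows: NAb positive; ADAb positive/NAb negative; NAb missing among ADAb positive. These sum to 100%.
- **All-bimekizumab base:** keep the denominator as it is and use the four groups the SAP already applies in 5.7.1.1 and in the efficacy figures, with ADAb negative shown as its own row and marked as not NAb tested. Add a row for participants whose overall ADAb status is missing under SAP 5.7.1.4 (more than one missing or inconclusive sample, the rest negative). The four groups alone give them no clear place.

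With 15 ADAb positive, 5 NAb positive and nothing missing, the all-bimekizumab base would read 15/30 = 50.0% ADAb negative, 5/30 = 16.7% NAb positive and 10/30 = 33.3% ADAb positive/NAb negative. The ADAb-positive base would read 5/15 = 33.3% and 10/15 = 66.7%.

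The cost is a few lines of SAP text and one table shell. No new data or assays are needed.
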